## **4. STUDY PROCEDURES**

### **4.1 Subject Recruitment and Screening**

#### **4.1.1 Primary objective (2.1), and secondary objective (2.2.1)**

Under a waiver of consent and HIPAA authorization, the study programmer will use electronic medical record data from KPWA to identify individuals who are due for cervical cancer screening based on previous screening history:

- 1) *Screening-adherent and coming due* (previously screened and due for screening within three months);
- 2) *Overdue* (never screened; or HPV and Pap co-test >5.25 years ago [or Pap alone >3.25 years ago]; or no past Pap and continuously enrolled at KPWA for ≥3.25 years)\*; and
- 3) *Unknown Prior Screening* (enrolled ≥6 months and <3.25 years, with no recorded screening history).

[figure not shown]
\*Individuals with due dates falling between March 2020-August 2020 will have randomization delayed for 12 months (March 2021-August 2021), because KPWA halted routine cervical cancer screening during these months of the COVID-19 pandemic. A 12-month delay in randomization of these individuals will (1) allow time for the delivery system to catch-up on the 6-month back log of screening visits, and (2) avoid potential misclassification of individuals as overdue solely due to their temporary inability to screen during the halted screening or due to their potential likely difficulty to schedule a screening visit during the expected surge in catch-up visits.

Clinical outreach provided by KPWA includes sending individuals a reminder letter that they are coming due approximately 60 days before their screening due date (for screening-adherent individuals), or repeat reminders every 60 days for individuals who are overdue (known to be overdue, or with an unknown screening history). The study programmer will use these clinical system outreach letters to identify eligible individuals. Each week, we will identify individuals who meet eligibility criteria and are mailed a clinical outreach letter. Eligible individuals will be identified, and a random sample will be randomized to intervention groups, stratified by screening history, as described below. Randomization will occur weekly over a 14-month recruitment period, and eligible individuals will be enrolled under a waiver of consent.

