## 5. STATISTICAL CONSIDERATIONS

### 5.1 Sample Size

[figure not shown]
Our sample size calculations are based on pairwise comparisons of screening rates and used preliminary data from the KPWA electronic medical record and observed data from the prior HOME trial. Using 2019 KPWA cervical cancer screening data, we estimate 37.1% of screening-adherent, 30.8% of Overdue, and 27.8% of individuals with Unknown screening histories will be screened within 6 months of randomization in the Education arm. Calculations assume a two-sided level 0.05 test, for differences in two proportions.

Our sample size was selected for adequate power to detect meaningful differences in cervical cancer screening rates between outreach strategies within each of the 3 target populations. Meaningful differences were selected based on estimates from the literature and observed data from the HOME trial. Small improvements in screening uptake are important, particularly if cost-effective and patient-centered; thus, the study is powered to detect relatively small differences between groups. Based on prior studies, we anticipate the Direct Mail strategy will have a greater impact on screening uptake than the Opt-In approach compared to Education; therefore, we have powered the study for a larger minimal detectable difference for the Direct Mail effect.

We estimated the sample size necessary to have 80% power to detect a 3% difference between Opt-In and Education and a 5% difference in screening completion between Direct Mail and Education. We anticipate that the Direct Mail strategy will have a larger impact on screening outcomes than the Opt-In approach, therefore we selected a larger detectable difference (and thus a smaller sample size needed)

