for the Direct Mail group. However, in the screening-adherent population, we computed the sample sizes needed for the 3% and 5% detectable differences respectively, and based the Education arm on the sample size necessary for the Education versus Opt-In comparison, which was larger than necessary for the Education versus Direct Mail comparison. Thus, we will have 80% power to detect a 4.1% difference for the Education vs. Direct Mail screening completion comparison. We selected sample size in the Usual Care group to detect a difference of 3.0% in screening completion between Usual Care and Education for the Screening-Adherent and Unknown populations. Given the smaller sample sizes in the intervention groups for the Overdue population, we were unable to achieve a least detectable difference (LDD) of 3.0% between Usual Care and Education. With a sample size of N=1398 in the Education group (based on an LDD of 3% for Education vs Direct Mail), we computed the detectable difference for a variety of sample sizes for the Usual Care group. We selected a sample size of N=5592 (4 Usual Care participants for each Education participant), because further increasing the Usual Care group led to diminishing improvements in LDD. This sample size yields a least detectable difference of 3.8%.

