**FIGURE 3: STEP randomization allocation by screening history**

Target sample sizes for each group, stratified by screening history, are shown in Figure 3, and will include randomizing a total of 13,735 Screening-Adherent (3879 Usual Care, 4171 Education, 4171 Opt-In, and 1514 Direct Mail); 8388 Overdue (5592 Usual Care, 1398 Education, and 1398 Direct mail); and 10,500 Unknown (3128 Usual Care, 3686 Education, and 3686 Opt-In).

Study enrollment will occur over a 14-month recruitment period. For all three study populations (Screening-Adherent, Overdue, and Unknown), the number of eligible individuals is estimated to exceed the number needed for the study. Therefore, to reach target sample size over the recruitment period, we will randomly select 231 Screening-Adherent, 142 Overdue, and 1777 Unknown individuals from the pool of all eligible individuals each week, for inclusion in the study. We will allocate each weekly sample to randomization groups as follows: Screening-Adherent (65 Usual Care, 70 Education, 70 Opt-In, and 26 Direct Mail), Overdue (94 Usual Care, 24 Education, and 24 Direct Mail), and Unknown (53 Usual Care, 62 Education, and 62 Opt-In). This sampling strategy maintains a consistent distribution across randomization arms over time, minimizing any potential impacts of temporal trends on group comparisons. If the number of eligible individuals in any given week is lower than the weekly target, the shortfall will be added to the target recruitment sample for the following week.

Beginning with wave 43, each randomization group (except Usual Care) will be further stratified by  $\leq 45$  years and  $>45$  years age groups, and then 1:1 randomized to receive age-targeted or non-age-targeted optimized Education brochure as part of their intervention materials (see Figure 2).

Our sample size estimates were based on data from 2019, before the COVID-19 pandemic which has impacted in-person cervical cancer screening. The sample size and recruitment plan described above is our *a priori* sampling strategy to achieve target sample size over the 14-month recruitment period. However, since the number of eligible individuals will vary with each data pull, and may be impacted by changes to care delivery, we will closely monitor recruitment and make necessary changes to ensure target sample sizes are met. Potential changes include the following:

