- 1) If the number of eligible individuals is consistently below the weekly target sample size, we will consider randomizing all eligible individuals rather than a sample, during weeks where there are more eligible individuals than the weekly target. The allocation fractions to randomization groups would remain the same as the original recruitment plan.
- 2) Since our comparison between Usual Care and Education is an exploratory aim, if the number of eligible individuals is considerably lower than anticipated, we will consider reducing the sample size allocated to Usual Care, to ensure target sample sizes in the Education, Opt-In, and Direct Mail groups are met.

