All analyses will be stratified by screening history population (Adherent, Overdue, and Unknown). All analyses will be based on the intention to treat principle, with individuals analyzed by the outreach approach arm to which they were randomly assigned. We will first conduct an overall chi-square test to assess differences in observed screening rates among randomization groups. The primary analysis will use a modified Poisson regression modeling approach to estimate the relative risk of screening completion associated with Direct Mail, and Opt-In strategies relative to Education (as appropriate by screening history population). A binary indicator for screening completion within 6 months (yes/no), as defined above, will be the dependent variable. Models will be fit using generalized estimating equations with an independent working correlation structure and robust standard error estimation to account for correlation between participants paneled to the same primary care provider. Models will adjust for baseline characteristics that differ by randomization arm. Models for Overdue participants will also be adjusted for overdue duration (<3 years and  $\geq 3$  years). The analysis for the outcome of screening initiation will use the same methods. The primary analysis will not include the Usual Care group, but secondary analyses will include this group, and will estimate the relative risk of screening outcomes for Education, relative to Usual Care.

Delays in screening impact time in compliance with screening recommendations and can also impact cancer outcomes. Thus, our analysis will also assess the time it takes to complete screening, defined as the number of days between randomization and screening completion, as a secondary outcome. We will use Kaplan-Meier log-rank tests to compare time to screening completion by randomization arm, with follow-up time censored at 6 months for non-completers. Analyses will be stratified by screening history population (Adherent, Overdue, and Unknown).

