Starting with recruitment wave 43, the original educational brochure was replaced with new brochures, revised based on focus group feedback. A new non-age-specific brochure, plus age-tailored ( $\leq 45$  and  $>45$  years of age) educational brochures were produced, and study participants, stratified by age group, were randomized to receive the non-age-specific or age-tailored materials. Using data from this embedded sub-study, we will investigate the effects of the revised education materials compared to usual care, and the effects of age-tailored materials compared to non-age-specific materials, on screening completion. This analysis will be limited to individuals randomized to the Usual Care or Education arms, starting with wave 43. We will use a generalized linear model approach, with log link function and Poisson error distribution to estimate the difference in screening completion rates. Indicators for usual care, non-age-specific materials, or age-tailored materials will be the exposure variables, and the binary outcome of screening completion (yes/no) will be the outcome. For the primary analysis, we will assume a constant effect of the revised education materials, and of age-tailoring, across all individuals, and the model will be fit using data from individuals in all screening history groups (Adherent, Overdue, and Unknown), and all ages. In secondary analyses, we will explore whether the effect of the non-age-specific and age-tailored materials differ by screening history or age ( $\leq 45$  and  $>45$ ) by adding indicator variables for these characteristics and interaction terms between these variables and the primary exposure variables.

Further analytic details of the above analyses, and additional secondary and exploratory analyses are provided in the study's Statistical Analysis Plan (SAP).

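### The brochure sub-study's main model pools three screening-history strata with unequal Usual Care:Education allocation and lists no history term, so its education-versus-usual-care estimate is modestly biased

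*Combined protocol and SAP*

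**What the plan says.** Protocol section 5.3.1 describes the sub-study analysis. It uses Usual Care and Education participants from wave 43 onward, in a Poisson model with log link whose listed exposure variables are usual care, non-age-specific materials and age-tailored materials. A constant effect is assumed, and "the model will be fit using data from individuals in all screening history groups (Adherent, Overdue, and Unknown), and all ages". Screening history and age come in only for secondary analyses, "by adding indicator variables for these characteristics and interaction terms between these variables and the primary exposure variables".

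Earlier in the same section the general rule is different: "All analyses will be stratified by screening history population (Adherent, Overdue, and Unknown)".

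Section 4.1.1 says that "a random sample will be randomized to intervention groups, stratified by screening history". Section 5.1 gives the weekly numbers: "Screening-Adherent (65 Usual Care, 70 Education, 70 Opt-In, and 26 Direct Mail), Overdue (94 Usual Care, 24 Education, and 24 Direct Mail)", and 53 Usual Care and 62 Education for Unknown. On expected completion in the Education arm it says: "we estimate 37.1% of screening-adherent, 30.8% of Overdue, and 27.8% of individuals with Unknown screening histories".

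On the main trial's Education versus Usual Care comparison, section 5.1 says: "We selected sample size in the Usual Care group to detect a difference of 3.0% in screening completion between Usual Care and Education". That applies to the Adherent and Unknown populations; the Overdue figure is 3.8%. Among possible recruitment changes it adds: "Since our comparison between Usual Care and Education is an exploratory aim", Usual Care numbers may be reduced.

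**The concern.** Randomization protects the comparison of Education with Usual Care within a history stratum. It protects a pooled comparison only if the allocation ratio is the same in every stratum or the analysis accounts for stratum. Here the ratio is close to 1:1 in two strata and about 4:1 in the third, and expected completion differs between strata. In a pooled model without a history term, the education coefficient combines the brochure effect with the difference in stratum mix.

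Assuming a constant effect does not help. A common risk ratio across strata does not make the baseline rates equal, and the baseline rates produce the bias.

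What is at stake is the estimate for one of the sub-study's two questions, revised education against usual care. Two other results are not at stake: the trial's primary analysis, which is within strata and omits Usual Care, and the age-tailored versus non-age-specific contrast, which is allocated 1:1 within each randomization group and age group.

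**Working it through.** **Inputs.** Weekly Usual Care (U) and Education (E) numbers, and expected Education-arm completion (p), all from section 5.1. Usual Care rates are not stated. Under the hypothesis of no brochure effect, the same p is used in both arms.

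| Stratum | U | E | U:E | p | Share of U | Share of E | E share − U share |
|---|---|---|---|---|---|---|---|
| Adherent | 65 | 70 | 0.93 | 37.1% | 30.7% | 44.9% | +0.142 |
| Overdue | 94 | 24 | 3.92 | 30.8% | 44.3% | 15.4% | −0.290 |
| Unknown | 53 | 62 | 0.85 | 27.8% | 25.0% | 39.7% | +0.147 |
| Total | 212 | 156 | | | | | |

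**The plan's own figure.** The 4:1 Overdue allocation is deliberate. With 5592 Usual Care, 1398 Education, an Education rate of 30.8%, 80% power and two-sided 0.05, the least detectable difference comes to 3.78% with Usual Care below Education. The stated 3.8% is reproduced, so rates and allocation are being read as the plan intends.

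**Expected estimate with no brochure effect.** A log-link model with exposure indicators only reproduces the crude pooled arm rates, Σ(n·p)/Σn:

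- Usual Care: (65×0.371 + 94×0.308 + 53×0.278)/212 = 67.801/212 = 31.98%
- Education: (70×0.371 + 24×0.308 + 62×0.278)/156 = 50.598/156 = 32.43%
- Difference +0.45 points; risk ratio 1.0142

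The target totals in place of the weekly numbers also give +0.45 points. A Poisson model fitted to the expected counts returns 1.0142 without history and 1.0000 with a three-level history term. Under a constant true effect the same factor applies: a true risk ratio of 1.05 would be estimated as about 1.065. Age-tailored versus non-age-specific is 1.0000 in both fits.

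**Dependence on stratum rates.** Bias in points = 0.142 × Adherent − 0.290 × Overdue + 0.147 × Unknown (rates in %). The rates below are assumptions, each varied with the other two at plan:

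| Assumed rate | Bias (points) |
|---|---|
| Overdue 25% | +2.1 |
| Overdue 28% | +1.3 |
| Overdue 30.8% (plan) | +0.45 |
| Overdue 32.4% | 0 |
| Overdue 35% | −0.8 |
| Adherent 34% | 0.0 |
| Adherent 40% | +0.9 |
| Adherent 48% | +2.0 |

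**If Usual Care is reduced.** Halving it in every stratum leaves the bias at +0.45. Halving it in Overdue only (94 to 47) gives a Usual Care rate of 32.32% and a bias of +0.12.

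**Effect on the test.** 13,735/231 = 59.5 and 8388/142 = 59.1, so about 60 waves, of which 18 (43 to 60) fall in the sub-study. That gives 18×212 = 3816 Usual Care and 18×156 = 2808 Education. Ignoring clustering by provider, the robust standard error of the log risk ratio is 0.0360, so the bias is ln(1.0142)/0.0360 = 0.39 standard errors. Two-sided rejection with no effect is then about 6.8% with robust variance. With the model-based Poisson variance (standard error 0.0438), which is too large for a binary outcome, it is about 2.6%.

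**The case against.** The strongest reply is that the covariate list may not be complete. Section 5.3.1 names exposure variables, not all model terms, and sends further detail to the SAP, whose text is not available here. The section also says models will adjust for baseline characteristics that differ by arm, and in the pooled sample history differs by arm by design. The first part stands as a caveat: the term may already be in the SAP. The second is weaker. That rule is written for the history-stratified main models, where history cannot differ by arm, and the sub-study paragraph does not invoke it. Its description of adding history indicators in secondary analyses implies that the main sub-study model lacks them.

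The clash with the general stratification rule can also be read as a later, specific exception. That is reasonable, but the text should say so, and an intended pooled model still needs the history term.

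On size, the bias at planning rates is small against the standard error, and the two-point cases need stratum rates that the documents do not give. The 3.0-point yardstick comes from the main trial's within-stratum design; the sub-study has no stated design difference. The exploratory or secondary label likewise belongs to the main-trial comparison, and section 5.3.1 calls the pooled model the sub-study's primary analysis. These points limit the weight of the finding.

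Finally, the planned secondary model would give history-specific estimates from which a careful reader could see the problem. That helps diagnosis but does not correct the headline estimate.

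**Conclusion.** The concern holds. As written, the sub-study's main model is inconsistent for the effect of revised education against usual care. At the plan's rates it shows +0.45 points (risk ratio 1.014) when there is no effect, about 15% of the 3.0-point main-trial design difference (0.45/3.0). The problem lies in the estimate more than in the test, whose size moves little at those rates.

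The figure assumes that Usual Care has the stated Education rates under no effect and that the weekly allocation runs as planned. The test-size figures also assume 18 waves. Section 5.1 notes that the rates predate the pandemic, so departures from them are plausible, and neither the sign nor the size of the bias can be fixed in advance. It is worth correcting because the correction is nearly free, but it does not touch the trial's primary conclusions.

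**What to change.** In the sub-study's primary model, include screening-history group as a three-level main effect, or estimate within history groups and combine. The common brochure effect can stay. Reconcile the sub-study paragraph with the general statement on stratification in section 5.3.1, and check the SAP: if it already has the term, correct only the protocol wording. State also that the robust variance specified for the main models applies to this Poisson model, since the paragraph is silent on variance. An age term is optional and is not needed to remove this bias.

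The cost is one line of text and two degrees of freedom, using a variable that already exists. In the no-effect fit with 18 waves, the robust standard error of the log risk ratio rises from 0.0360 to 0.0376, about 4%. No further participants or data are needed.

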### 5.3.2 Analysis plans relevant to secondary objective one (2.2.1)

We will conduct a cost-effectiveness analysis of the outreach approaches for in-home HPV self-sampling kits with the incremental cost-effectiveness ratio (ICER) defined as the incremental cost per incremental increase in number of individuals who successfully achieve cervical cancer screening completion as defined by our primary study outcome, which includes appropriate follow-up of other-HR HPV positive HPV self-sampling kit results. The primary economic outcome will be an ICER. For screening-adherent individuals, ICERs will reflect comparisons between a) Opt-In and Education, b) Direct Mail and Education, and c) Direct Mail and Opt-In with Opt-In as the reference strategy. For Overdue individuals, the ICER will compare Direct Mail to Education. For individuals with Unknown screening histories, the ICER will compare Opt-In to Education. Within each screening status group, we will also be able to generate an ICER for Education compared to Usual Care. The study design precludes a comprehensive ICER comparing a single strategy (or set of strategies) to Education or Usual Care across all participants. Costs and screening outcomes will be varied in univariate, multivariable, and/or probabilistic sensitivity analyses as appropriate in Excel-based and Stata-based programs. Discounting and inflation adjustments will not be applied to costs or outcomes because of the 6-month assessment period. The STEP study will allow us to inform the delivery system with screening uptake projections, screening strategy selection, and the relative cost implications of switching from in-clinic to in-home testing, which may differ by prior screening behavior.

### 5.3.3 Analysis plans relevant to secondary objective two (2.2.2)

We will use data from the interviews and focus groups to evaluate participants' preferences for, and satisfaction with, in-home HPV screening and barriers to follow-up of abnormal screening results. Surveys administered during the interviews and embedded in focus groups discussions will measure knowledge, perceived risk, efficacy beliefs about in-home HPV screening, trust in kit, self-efficacy, kit experience, reasons for not returning kit, screening test preference, future screening intentions, and patient-centered communication around screening.

